8.9.1. Study closure/uninterpretability of results

The planned study closure is October 2015, time of the final report. Medical records will be abstracted until April 2015 unless patients discontinue or withdraw from the study. It is foreseen that study enrolment will stop upon reaching circa 300-450 patients or at the end of abstraction whichever comes first.

The study can be terminated at any time for any reason by GSK. The investigator may be informed of additional procedures to be followed in order to ensure that adequate consideration is given to the protection of the patient's interests. The investigator will be responsible for informing IECs of the early termination of the study. The early termination of the study is considered a major amendment; therefore, the relevant competent authorities will be notified before a final decision is made and approval for termination is granted.

8.10. Other Aspects: Changes to the Protocol

Changes to the protocol will be documented in written protocol amendments. Major (i.e., substantial, significant) amendments will be approved by the relevant competent authorities (as applicable) and will usually require submission or notification to the relevant independent ethics committees (IECs) for approval or favourable opinion, if applicable. In such cases, the amendment will be implemented at the site only after approval or favourable opinion has been obtained.

Minor (non-substantial) protocol amendments, including administrative changes will be submitted to the relevant IECs or regulatory authorities where required by pertinent regulations. Any amendment that could have an impact on the patient's agreement to participate in the study requires the patient's informed consent prior to continued participation in the study.

9. PROTECTION OF HUMAN SUBJECTS

To ensure the quality and integrity of research, this study will be conducted under the Guidelines for Good Pharmacovigilance Practices (GVP) and Good Pharmacoepidemiology Practices (GPP) issued by the International Society for Pharmacoepidemiology (ISPE), the Declaration of Helsinki and its amendments, and any applicable national guidelines.

In applicable countries, the protocol and the proposed ICF must be reviewed and approved by a properly constituted IEC before study start. Prior to study start, the investigator (investigator) is required to sign a signature page confirming his/her agreement to conduct the study in accordance with these documents and all of the instructions and procedures found in this protocol and to give access to all relevant data and records to monitors, auditors, Quality Assurance (QA) representatives, or designated agents of GSK, IECs and Competent Authorities as required.

9.1. Patient Information and Informed Consent

Patients treated with REVOLADE in EU hospitals/wards including office based participating in this study will be identified after being discharged from the hospitalization involving treatment with REVOLADE by periodic query of medication records. At the national or local level, ICFs will be sent to each of these patients (or to next of kin for those patients who are deceased), and only consenting patients will be enrolled in the study.

Informed consents must be obtained before conducting any study-specific procedures (i.e. all of the procedures described in the protocol). The process of obtaining informed consent, including the identity of the person who conducted the consenting process, should be documented in the patient medical records. The date when a patient's informed consent was actually obtained will be captured in the eCRF.

Each patient (or legal representative if applicable) must sign the ICF(s) before any data is collected. A copy of each signed ICF must be provided to the patient or the patient's legally authorised representative. All signed and dated ICFs must remain in each patient's study file and must be available for verification by study monitors at any time.

The ICF(s) should be revised whenever there are changes to procedures outlined in the informed consent or when new information becomes available that may affect the willingness of the patient to participate. For any updated or revised ICF(s), the medical record for each patient should document the ICF process and that written informed consent was obtained for the updated/revised ICF(s) for continued participation in the study.

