8.2. Setting

The REVOLADE DUS will include approximately 300 to 450 patients being treated with REVOLADE at approximately 18-21 hospital/ward or office based sites in selected EU Member States. France, Germany and Spain are the primary targeted countries, based on the most frequent REVOLADE use approximated from IMS prescription sales data. To meet the recruitment goal, additional EU country(ies) and sites may be added based on multiple factors including use of REVOLADE (compared to use approximated by sales data), available prescription data, and favourable regulatory environment to conduct observational studies.

To avoid overrepresentation of any individual sites or countries, recruitment may be capped during the study at site or country level.

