8.2.1. Inclusion Criteria

To be enrolled into the study, patients must meet the following criteria:

- Documented past treatment with REVOLADE between the period immediately after first approval/launch and September 2014 (i.e., dispensed at least once by the pharmacy and patient received at least one dose) for whatever reason
- Patient (or a legal representative) has provided a written informed consent to participate in the study

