8.2.4. Site Selection

The study will be implemented at approximately 18- 21 sites in selected countries in the EU (six or seven sites per country) by selecting sites that are geographically dispersed to best represent different practices across regions/provinces within the selected EU Member States. Also, selection of study sites will be determined at the country level in order to obtain a representative sample of sites reflective of the treatment patterns within each country. Site qualification and selection criteria will include: type of physician/hospital, geographic location (e.g., rural, urban), practice setting (clinics, academic setting, and reference centre), capture area, estimated eligible patient availability, number of patients seen in previous year, availability and number of eltrombopag pharmacy records), and staffing availability.

The Study will target a representative sample of physicians who prescribe REVOLADE, irrespective of the indication. These include hematologists, oncologists, virologists, hepatologists, internal medicine and other specialists from the hospital or office based setting. The data collected in the Study will be used to determine the characteristics of patients for whom REVOLADE is prescribed and to understand if it is being prescribed in accordance with the product labelling.

The site and investigator identification, selection and recruitment process will be detailed in the Site Recruitment Plan document, which will be developed at study start-up. This document will describe the process for site identification, site recruitment process with flow chart, site qualification process via the study specific site qualification questionnaire. In addition, this document will describe the process how to contact and conduct follow-up activities of identified sites and investigators. Potential risks to the plan will be identified early in its development to ensure that proper risk mitigation measures are put in place to ensure achievement of site enrolment objectives.

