8.2.5. Patient Enrolment

Since the purpose of this study is to evaluate routine clinical use of REVOLADE, patients will be identified based on the prescription of REVOLADE rather than on a specific diagnosis or condition.

The study population will consist of patients who have been prescribed REVOLADE for whatever reason according to the data retrieved in the medical records, provided they gave informed consent, had not or were not currently participating in a REVOLADE clinical trial, and used REVOLADE within the time period defined below. The medical records of all patients treated with REVOLADE in a participating centre will be reviewed for inclusion in this retrospective study, until the overall target number of at least 300 patients has been reached, irrespective of indication, medical condition, dose and treatment duration.

Patients are eligible for inclusion in study if their first prescription of REVOLADE was given between the period immediately after REVOLADE launch date and the start date for data abstraction i.e., September 2014. Patients who have been first prescribed REVOLADE after September 2014 will not be included in the study in order to ensure that study procedures do not influence prescribing practices. Informed consent will be

obtained as per country-specific regulations. Assuming the country-based first launched dates of REVOLADE in its initial chronic ITP indication (see Figure 1), the eligibility periods in the three selected countries thus span between January 2011 and September 2014 for France, April 2010 and September 2014 for Germany and December 2010 and September 2014 for Spain.

The earliest launch date for the chronic HCV-associated thrombocytopenia indication in these countries can be no sooner than September 2013, corresponding to the date it was approved by the European Commission. Considering that approval of HCV-associated thrombocytopenia indication was just recently, the number of expected HCV-associated thrombocytopenia patients therefore will be very small.

It is expected that approximately six or seven sites will be identified per country, and that up to 50 medical records will be abstracted at each site accounting for a total of 300 to 450 patients for the study.

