ANNEX 2. DISPENSING SYSTEMS IN SELECTED EU MEMBER STATES

Distribution of REVOLADE in Germany

There are two channels of REVOLADE distribution in Germany- 1) a hospital based channel and 2) a retail based channel.

- 1. In the first hospital based channel, doctors that work in a hospital can prescribe REVOLADE and then patients can fill a prescription either at a hospital based pharmacy (in-patient) or public pharmacy including pharmacy specialized in oncology field (out-patient). In this channel, an order placement for REVOLADE and product delivery occurs directly between the GSK order center and hospital based pharmacies or hospital supplying pharmacies in this case.
- 2. In the second retail pharmacy channel, an office based hematologists and oncologists can prescribe REVOLADE and then patients can fill a prescription through public pharmacies or pharmacies specialized in oncology. In this second channel, an order placement for REVOLADE and product delivery occurs through a wholesaler, which then can deliver REVOLADE to public pharmacies and pharmacies specialized in oncology.

It is critical to point out that doctors or Institutions can't order REVOLADE directly from the GSK order center. They must place an order through a pharmacist. More importantly, considering the German data privacy law, pharmicists are not allowed to disclose any information including the physician's or patient's name to anybody. Therefore, patients prescribed Revolade through both of these channels will be identified for the study.

Distribution of REVOLADE in Spain

Currently, there is a single channel of REVOLADE distribution in Spain and this is a hospital based channel. Doctors including hematologists, oncologists and hepatologists that work in a hospital can prescribe REVOLADE and then patients can fill a prescription at a hospital based pharmacy. An order placement for REVOLADE and product delivery can occur directly between the GSK order center and hospital based pharmacies. In addition, the pharmacists records can identify prescribers of REVOLADE in the entire hospital, not only hematology/oncology or gastroenterology and hepatology department. Therefore, patients who received REVOLADE will be identified through the hospital based physicians and hospital based pharmacists.

Distribution of REVOLADE in France

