In France, the distribution of Revolade occurs through a hospital and private pharmacy including hematologists, channel. Doctors oncologists, hepatologists. gastroenterologists and internal medicine physicians based at university hospitals, public hospitals, and private hospitals can prescribe Revolade and then patients can fill a prescription at a hospital and private pharmacy. It is critical to point out that considering the French privacy rules, pharmacists are not allowed to disclose any information including the physician's or patient's name to anybody. Therefore, medical records of patients received Revolade through university hospital or public or private based hospital will be used for review in the study.

Name of main author of study protocol:
Date: 23/05/2014
Signature:

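### Section 9.1 ties patient identification and consent to hospital discharge, so as written never-admitted users have no route in, contrary to Sections 8.2, 8.2.4, 8.2.5, 8.3.3 and Annex 2

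*Protocol*

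**What the plan says.** The first sentence of Section 9.1 has as its subject "Patients treated with REVOLADE in EU hospitals/wards including office based participating in this study". It says that these patients "will be identified after being discharged from the hospitalization involving treatment with REVOLADE by periodic query of medication records". The next sentence sends consent forms to each of these patients, or to next of kin if deceased, and limits enrolment to those who consent. Written consent is also an inclusion criterion in Section 8.2.1.

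The sections that define the sample describe a wider group:

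- Section 8.2 plans "approximately 18-21 hospital/ward or office based sites in selected EU Member States".
- Section 8.2.4 targets prescribers including "internal medicine and other specialists from the hospital or office based setting".
- Section 8.2.5 bases identification on the prescription of REVOLADE and adds: "The medical records of all patients treated with REVOLADE in a participating centre will be reviewed for inclusion in this retrospective study". It sets no hospitalisation condition.
- Section 8.3.3 records a discharge date only where the patient was hospitalised.
- Annex 2 describes a German retail channel in which "an office based hematologists and oncologists can prescribe REVOLADE and then patients can fill a prescription through public pharmacies", and concludes that patients from both the hospital and the retail channel are to be identified.

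**The concern.** Section 9.1 is the only place that states how a patient moves from being identified to receiving a consent form. If identification waits for a discharge, a patient who has never been admitted does not reach that step. Such patients are to be expected: the protocol describes an oral drug taken once daily, and it plans office-based sites.

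Both objectives, the pattern of use by condition and age and the description of patients in routine practice, depend on who is found. So does the proportion of off-label use, on which Section 8.5.1 bases the study size. If admitted and never-admitted users differ in indication or label status, a sample found through discharges does not describe users as a whole.

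The conflict also allows sites to work differently. Section 8.1 has investigators queried for treated patients, Section 8.2.5 has all records reviewed, and Section 9.1 waits for discharge. Section 9 has each investigator sign to follow all procedures in the protocol. Two sites could each claim compliance while applying different case-finding rules, which would weaken the by-country results planned in Section 8.7.3.

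**Working it through.** **The texts side by side**

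| Question | Section 9.1 | Elsewhere |
|---|---|---|
| What triggers identification? | Discharge from a hospitalisation involving REVOLADE | Prescription of REVOLADE (8.2.5) |
| Whose records are considered? | Discharged patients | All treated patients at the centre (8.2.5) |
| Is admission assumed? | Yes | No: discharge date only if hospitalised (8.3.3) |
| Are office-based users covered? | Named, but under a discharge trigger | Yes (8.2, 8.2.4; Annex 2 for Germany) |

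Naming office-based patients in 9.1 does not resolve the conflict, because a discharge trigger cannot apply to someone who was never admitted.

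**Who is affected.** Annex 2 describes office-based prescribers only for Germany; for Spain and France it describes hospital-based prescribers. The office-based gap is therefore mainly German. Hospital outpatients who were never admitted are affected in all three countries.

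**The plan's own precision figure.** Section 8.5.1 gives 2.1 points at 400 patients and a 5% rate. The normal approximation reproduces it: 1.96 × √(0.05 × 0.95 / 400) = 1.96 × 0.0109 = 0.0214, or 2.1 points, giving 2.9% to 7.1%.

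**Bias if 9.1 is followed literally at every site.** Let s be the share of users never admitted, p_A the off-label rate in admitted users and p_N the rate in never-admitted users.

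- Rate among all users: (1 − s) p_A + s p_N
- Rate expected in a discharge-based sample: p_A
- Bias: p_A − [(1 − s) p_A + s p_N] = s (p_A − p_N)

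The protocol gives none of s, p_A or p_N, so the values below are assumptions that show a range.

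| Assumed s | Bias for a 3-point difference | Difference that gives 2.1 points of bias |
|---|---|---|
| 0% | 0 | none |
| 30% | 0.3 × 3 = 0.9 points | 2.1 / 0.3 = 7.0 points |
| 50% | 0.5 × 3 = 1.5 points | 2.1 / 0.5 = 4.2 points |
| 70% | 0.7 × 3 = 2.1 points | 2.1 / 0.7 = 3.0 points |

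In the last row, with a rate of 5% among all users, a discharge-based sample would be expected to show 7.1% or 2.9%, depending on the sign of the difference. Those are the limits of the plan's own interval. A larger sample would not reduce the error. If sites follow 8.2.5, the bias from this source is nil.

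**The case against.** The strongest reply is that this is one clause in a consent section. The abstract and Sections 8.1, 8.2, 8.2.4, 8.2.5, 8.3.3 and 8.9 agree with one another and set no hospitalisation condition, and 9.1 itself names office-based patients. A site would more naturally take its enrolment rule from 8.2.5. This stands as a reason not to call the exclusion settled. It does not remove the contradiction, because 9.1 is the text that tells a site whom to send consent forms to.

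A second reply is that Section 8.2.5 requires a screening log of all treated patients, with reasons for non-participation, expressly to assess representativeness. Never-admitted patients left out should appear on it. That stands as a means of detection. But the log holds birth year, gender, participation and reason for non-participation, not indication, label status or admission. It could reveal the gap but could not correct the off-label estimate.

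A reader might also infer that the inclusion criterion, "dispensed at least once by the pharmacy and patient received at least one dose", excludes outpatients as well, since Annex 2 says for France that "pharmacists are not allowed to disclose any information" and states the same limit for Germany. The documents do not support this. The criterion does not restrict the type of pharmacy or ask for a pharmacy-issued record, and every route in Annex 2 ends at a pharmacy, so outpatients and office patients can meet it. Dispensing may be harder to document in some charts, but that is a practical difficulty and not an exclusion.

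**Conclusion.** The protocol contradicts itself on how patients are found. As written, 9.1 gives never-admitted users no identification or consent route, while the sampling sections and Annex 2 count on their inclusion. Sites that follow 9.1 would select hospitalised users; sites that follow 8.2.5 would not.

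Neither the size nor the direction of the effect can be derived from the document. It runs from nil upward. It reaches the stated precision of 2.1 points only under assumptions such as a 70% never-admitted share with a 3-point difference, or 50% with 4.2 points.

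Two stronger conclusions are tempting and not supported. One is that outpatients and office-based users are definitely shut out: other sections plainly include them, so this is a conflict to reconcile. The other is that the whole German retail channel would be lost: Annex 2 says that channel will be covered, and even under the literal reading a retail-channel patient may have been admitted while on the drug.

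The sentence should be corrected because, if followed, it would bias case finding for both objectives.

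**What to change.** Replace the first sentence of Section 9.1 with the rule of Section 8.2.5. Suggested content: each site lists every inpatient or outpatient with a REVOLADE prescription in the eligibility window, regardless of hospitalisation, and consent forms are sent to all patients on the list, or to next of kin where the patient has died. The rest of 9.1 can stay. The inclusion criteria in Section 8.2.1 and in the abstract need no change for this point.

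The cost is a wording change in one section. If the protocol has already gone to ethics committees, it would be handled as an amendment under Section 8.10. Sites following 9.1 literally would have more consent forms to send, but Section 8.2.5 already implies that work.

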9.2. Patient Confidentiality

In order to maintain patient confidentiality, each patient will be assigned a patient identification number upon study enrolment. This patient number will be used in place of patient name for the purpose of data analysis and reporting. Medical record number or other local reference identifiers are not collected as part of the study database. All parties will ensure protection of patient personal data and will not include patient names on any study forms, reports, publications, or in any other disclosures, except where required by law. In accordance with local regulations in each of the study countries, patients will be informed in the ICF about data handling procedures. Data protection and privacy regulations will be observed in capturing, forwarding, processing, and storing patient data.

All patient information will be handled in accordance with national data protection standards and the EU Directive 2002/58/EC (July 12, 2002) on the processing of personal data and the protection of privacy in the electronic communication sector. Every effort will be made to protect participant confidentiality according to the Directive 95/46/EC on the protection of individuals with regard to the processing of personal data.

9.3. Independent Ethics Committee

Consistent with local regulations and prior to enrolment of patients at a given site, the study protocol will be submitted together with its associated documents (e.g., ICF(s)) to the responsible IEC for its review. Patient enrolment will not start at any site before GSK has obtained written confirmation of a favourable opinion/approval from the relevant central or local IEC. The IEC will be asked to provide documentation of the date of the meeting at which the favourable opinion/approval was given that clearly identifies the study, the protocol version, and the ICF version reviewed.

Before implementation of any substantial changes to the protocol, protocol amendments will also be submitted to the relevant IEC in a manner consistent with local regulations. Pertinent safety information will be submitted to the relevant IECs during the course of the study in accordance with local regulations and requirements. It is the responsibility of the investigator to have prospective approval of the study protocol, protocol amendments, ICFs, and other relevant documents, if applicable, from their local IRB/IEC and provide documentation of approval to GSK. All correspondence with the IRB/IEC should be retained in the Investigator Site File.

Should the study be terminated early for any unanticipated reason, the investigator will be responsible for informing the local IRB/IEC of the early termination.

